## Appendix A3: Derived Outcome Variables

### Primary Outcome

The primary outcome is intention to treat 90 day all cause in-hospital mortality, where in-hospital includes study hospital and LTAC. Patients who are discharged home (defined as residence prior to admission) prior to day 90 will be assumed to be alive at day 90. It may be necessary to account for patients who are still in the hospital with less than 90 days of follow up. This will be accomplished using the Kaplan Meier day 90 mortality point estimates with all patients who are discharged home or still alive at day 90 censored at day 91, which is beyond the last possible day of death.

If a patient has no data entered for the primary outcome then a censoring date is determined from the maximum date or study day on the available ACTIVITY, SOFA, VENT, MMT, TERMINATION, ICU History, Study Initiation and Drug Dosage, Protocol Deviation, AE, and BRICE forms.

### ICU acquired weakness

Patients will be defined as having ICU acquired weakness if their Medical Research Council (MRC) MMT score is < 48 (or mean MRC < 4 for each muscle group tested).

### Hospital mortality to day 28

Death prior to discharge alive from study hospital will be counted as hospital mortality. Patients whose final status is unknown but who are known to be alive on study day 28 based on known event dates on the termination form will be counted as alive. Patients with insufficient follow up to determine this outcome will be treated as missing data.

### Ventilator free days to day 28

Ventilator free days to day 28 are defined as the number of days from the time of initiating unassisted breathing to day 28 after randomization, assuming survival for at least two consecutive calendar days after initiating unassisted breathing and continued unassisted breathing to day 28. If a patient returns to assisted breathing and subsequently achieves unassisted breathing to day 28, VFDs will be counted from the end of the last period of assisted breathing to day 28. A period of assisted breathing lasting less than 24 hours and for the purpose of a surgical procedure will not count against the VFD calculation. If a patient was receiving assisted breathing at day 27 or dies prior to day 28, VFDs will be zero. Patients transferred to another hospital or other health care facility will be followed to day 28 to assess this endpoint.

### Organ failure free days to day 28

Organ failure is defined as present on any date when the most abnormal vital signs or clinically available lab value meets the definition of clinically significant organ failure according to SOFA scores. Patients will be followed for development of organ failures to death, hospital discharge or study day 28, whichever comes first. Each day a patient is alive and free of a given organ failure will be scored as a failure-free day. Any day that a patient is alive and free of all organ failures will represent days alive and free of all organ failure.

Variables	SOFA Score				
	0	1	2	3	4
Coagulation Platelets x 10  /µL	>150	</=150	</=100	</=50	</=20
Liver Bilirubin, mg/dL	<1.2	1.2-1.9	2.0-5.9	6.0-11.9	>11.9
Cardiovascular Hypotension	No hypotension	Mean arterial pressure <70 mmHg	Dop</=5 or dob (any dose) ‡	Dop >5, epi</=0.1, or norepi </=0.1‡	Dop >15, epi >0.1, or norepi >0.1‡
Renal Creatinine, mg/dL or urine output, ml/d	<1.2	1.2-1.9	2.0-3.4	3.5-4.9 or <500	>4.9 or <200

\*Norepi indicates norepinephrine; Dob, dobutamine; Dop, dopamine, Epi, epinephrine.

†Values are with respiratory support.

‡Adrenergic agents administered for at least one hour (doses given are in µg/kg/min)

We define a clinically significant organ failure as a new SOFA score of  $\geq 2$ .

We treat post-ICU SOFA as normal (i.e. defining organ dysfunction as abnormal SOFA in an ICU); post-ICU means getting out and staying out of ICU; patients are still at risk and have SOFA scores in intervals between ICU readmissions.

Carry forward until home date, death date, last known date in ICU+1, or day29, whichever comes first; patient status decides organ failure free if both status information and SOFA data are available.

We carry last observation forward for any missing data except baseline P/F. Carry forward vasopressors yes/no if taking any vasopressors and missing y/n. Carry forward vasopressor doses if taking this drug and missing dose.

If a patient has missing data at baseline, then the patient would have missing SOFA components, but the total will be the sum of available components scores instead of missing.

Notes: LOCF carries forward each sofa variable rather than carrying forward the computed scores.

### ICU-free days at day 28

Patient will be followed until death, study hospital discharge or study 28, whichever comes first. Any day a patient is alive and out of ICU will be scored as an ICU-free day. There is no penalty for readmission.

#### Hospital-free days at day 28

Hospital free days are counted from hospital discharge through day 28. A patient who is discharged from the study hospital on day 28 is assigned one hospital free day. A patient who is discharged from the study hospital after day 28 is assigned zero hospital free days. A patient who dies prior to day 29 is assigned zero hospital free days.

#### Paralysis recall, in-hospital

Paralysis recall assessment will be monitored once during hospitalization in all patients, using a modified Brice questionnaire. Paralysis recall will be counted if a patient answered "Yes" to "Do you remember anything between going to sleep and waking up?" and "unable to move or breathe". Paralysis recall can be indicated in both AE and Brice forms. We gather information from both places and treat missing as "NO" if a patient has an open BRICE form.

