#### Other Reference Measurements

1. Manual muscle strength testing (MMT) screen and assessment on day 7, 14, 21 28 or until hospital discharge.
2. Assessment of gross motor movement on study day 3.
3. Paralysis recall assessment, in both study arms, one time during study hospitalization, using a modified Brice questionnaire [22, 23].

To facilitate the ability of the patient to interact appropriately with the above measures, sedative agents will be titrated according to the institution's sedation protocol. The MMT and the Modified Brice questionnaire will be conducted in patients who meet the awakening and comprehension criteria. Awakening and comprehension will be determined based upon the response of the patient to five commands ("open/close your eyes," "look at me," "open your mouth and stick out your tongue," "nod your head," and "raise your eyebrows when I have counted to five"). If the patient can respond appropriately to all five of these orders, the patient will be considered awake and able to comprehend and the above measures will be attempted to be obtained.

Additionally, prior to conducting the MMT the patient will be assessed for injuries or medical devices that would preclude the MMT assessment and for any safety barriers to strength training such as unstable shock, profound hypoxemia, unstable spine or airway, nonresponsive to verbal command (RASS -4 or -5). The Manual Muscle strength testing uses the MRC (Medical Research Council) score evaluates muscle strength with very good interobserver agreement, and was used in the ACURASYS trial [2, 32]. Introduced in 1970, the Brice questionnaire is a reliable and efficient method of detecting recall after sedation or general

anesthesia. This questionnaire avoids falsely identifying pre-sedation memories and experiences [22, 23].

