# 11 ADVERSE EVENTS

## 11.1 SAFETY MONITORING

Assuring patient safety is an essential component of this protocol. Each participating investigator has primary responsibility for the safety of the individual participants under his or her care. The Investigators will determine daily if any adverse events occur during the period from enrollment through **study day 7** (five days after infusion of study drug) or ICU discharge, whichever occurs first.

The following adverse events will be collected in the adverse event case report forms:

- Serious adverse events
- Nonserious adverse events that are considered by the investigator to be related to study drug or study procedures or of uncertain relationship (Appendix C2)
- Adverse events that lead to permanent discontinuation of the study drug infusion
- Hypersensitivity reactions to cisatracurium, severe prolonged bradycardia (heart rate < 50 for > 30 minutes), and paralysis recall
- Hypotension or pneumothorax, considered by the investigator to be related to high PEEP, or of uncertain relationship.

A clinical trial adverse event is any untoward medical event associated with the use of a drug or study procedure in humans, whether or not it is considered related to a drug or study procedure.

After randomization, adverse events related to protocol procedures or occurring after the patient receives the first dose of study drug must be evaluated by the investigator. If the adverse event is judged to be reportable, as outlined above, then the investigator will report to the CCC their assessment of the potential relatedness of each adverse event to protocol procedure or study drug via electronic data entry. Investigators will assess if there is a reasonable possibility that the study drug or procedure caused the event, based on the criteria outlined in Appendix C2. Investigators will also consider if the event is unanticipated or unexplained given the patient's clinical course, previous medical conditions, and concomitant medications.

If a patient's treatment is discontinued as a result of an adverse event, study site personnel must report the circumstances and data leading to discontinuation of treatment in the adverse event case report forms.

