**Additional Derived Variables**

**Barotrauma**

Barotrauma includes pneumothorax and pneumomediastinum, which can be indicated in both AE and Termination forms. We gather the information from both places and treat missing as "NO".

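### Coding missing paralysis recall as NO on any open Brice form counts non-response as a negative, which can only lower the recorded recall rate or leave it unchanged

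*SAP*

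**What the plan says.** SAP Appendix A3, under paralysis recall, names two sources: "Paralysis recall can be indicated in both AE and Brice forms". The event needs two answers. The first is a positive reply to the memory question: "Paralysis recall will be counted if a patient answered 'Yes' to 'Do you remember anything between going to sleep and waking up". The second is a report of having been unable to move or breathe. The missing-data rule follows: "We gather information from both places and treat missing as" NO when the patient has an open Brice form. The SAP does not say what makes a form open. It plans no count of unanswered items and no sensitivity analysis for this outcome. Appendix A1 lists recall as a binary safety variable compared by Fisher's exact test.

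SAP 2.7 says that available data are analysed without imputation apart from a few exceptions noted in an appendix, and that all proposed analyses are valid when data are missing at random (MAR).

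Protocol 3.9.2 (item 11) says recall is assessed once during hospitalization in all patients. Protocol 6.3.2, Other Reference Measurements, is narrower: "The MMT and the Modified Brice questionnaire will be conducted in patients who meet the awakening and comprehension criteria". Protocol 11.1 also collects recall as an adverse event, in a list that includes "severe prolonged bradycardia (heart rate < 50 for > 30 minutes), and paralysis recall". On timing it says "The Investigators will determine daily if any adverse events occur during the period from enrollment through" study day 7, or ICU discharge if that comes first.

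**The concern.** An open form is not an answer. If a patient starts the questionnaire and does not reply to the recall items, or if a form is created and never completed, the rule enters that patient in the denominator as assessed and free of recall. Nothing in the rule works the other way, so any error lowers the rate of a harm.

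Protocol 3.6 (item 6) criticises the earlier trial because paralysis recall was not determined, so this is evidence the trial set out to supply. The trial is unblinded, and sedation targets differ by arm during the first 48 hours, so unequal non-response is conceivable. It would then bias the comparison as well as the rates.

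**Working it through.** The documents state no recall rate, blank rate or power for this outcome, so there is no figure of the plan's own to reproduce. Every rate below is an assumption chosen to show direction and scale.

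**Notation**, among patients with an open Brice form:
- p = true recall rate
- m = share whose items are truly unanswered (valid skips excluded), unrelated to recall unless stated
- c = share of unanswered patients with recall who are caught on the AE form

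**Recorded rate under the SAP rule.** Answered forms contribute p(1 - m) and AE-caught blanks contribute p × m × c. The sum is p × (1 - m × (1 - c)), which is at most p. It equals p only if m = 0 or c = 1.

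**Size with c = 0:**

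| p | m = 5% | m = 10% | m = 20% | m = 30% |
|---|---|---|---|---|
| 2% | 1.9% | 1.8% | 1.6% | 1.4% |
| 5% | 4.75% | 4.5% | 4.0% | 3.5% |

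With p = 2% and m = 30%, c = 0.5 gives 0.02 × (1 - 0.15) = 1.7%, and c = 1 gives 2.0%.

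**The MAR claim.** Completely random blanks are a special case of MAR. Leaving them missing gives p(1 - m)/(1 - m) = p. Coding them NO gives p(1 - m). The rule is therefore biased in a case where SAP 2.7 claims validity.

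**Arm comparison, equal blanks.** True rates of 3% and 1% with m = 20% in both arms are recorded as 2.4% and 0.8%. The difference shrinks from 2.0 to 1.6 percentage points. By a normal approximation with an assumed 400 forms per arm, power falls from 52% to 44%. Leaving the blanks missing also gives 44%, so the cost of the rule is bias, not extra loss of power.

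**Arm comparison, unequal blanks.** Take a true rate of 5% in both arms, with 20% blank in the active arm and 5% in control. The recorded rates are 0.05 × 0.80 = 4.0% and 0.05 × 0.95 = 4.75%. The ratio is 0.84, an apparent advantage for active where none exists.

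**Limit of complete-case analysis.** Suppose patients with recall are blank more often (30% against 10%, p = 5%). The SAP rule gives 0.05 × 0.70 = 3.5%. Complete cases give 0.035/(0.035 + 0.95 × 0.90) = 0.035/0.890 = 3.9%. That is closer but still low, so a bound is needed as well.

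**Choice of denominator.** Take 1000 open forms, p = 2% and m = 30%: 700 answered (14 with recall) and 300 blank (6 with recall).

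| Analysis | AE form catches 3 of the 6 | AE form catches all 6 |
|---|---|---|
| SAP rule | 17/1000 = 1.7% | 20/1000 = 2.0% |
| Answered plus AE-reported | 17/703 = 2.4% | 20/706 = 2.8% |
| Determinable Brice answers only | 14/700 = 2.0% | 14/700 = 2.0% |

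Admitting blank patients to the denominator only when they are positive overstates the rate.

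**The case against.** The case for the rule has real substance.

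- **Valid skips.** If the memory question is answered No, a blank second item correctly means NO, and this may be what the rule was written for. That stands. The SAP does not confine the rule to this case, so skips and non-response are coded alike.
- **Screening.** Only patients who respond correctly to five commands receive the questionnaire, and patients without an open form are not set to NO. This should limit non-response. It does not remove it, since Protocol 6.3.2 promises only an attempt, and the undefined word open leaves room for forms that were never completed.
- **AE back-up.** Recall reported on the AE form is counted even if the Brice form is blank, so c may exceed zero. The back-up is partial: routine AE collection stops at study day 7 or ICU discharge, while the Brice assessment can come at any time in the hospital stay.
- **SAP 2.7.** A reader might infer that the rule contradicts this section. It does not, because 2.7 allows appendix exceptions. That 2.7 points to Appendix B while the rule sits in A3 is a labelling matter. What fails is the claim of validity under MAR.
- **Barotrauma.** A reader might extend the point to this variable, where the SAP says "We gather the information from both places and treat missing as" NO. That rule differs. It has no open-form condition and concerns an event recorded on the AE and Termination forms, not a patient interview. Setting every blank Termination item to missing could discard events reported on the AE form. No change to barotrauma follows from this point.

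**Conclusion.** The point holds in a limited form. The SAP codes true non-response on a listed secondary safety outcome as a confirmed negative. The direction is certain: the recorded rate is lowered or unchanged. The size cannot be found from the documents. The fall from 2% to between 1.8% and 1.4% rests on an assumed true rate, assumed blanks of 10% to 30% unrelated to recall, and no AE capture.

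A reader might conclude that recall will be understated, or that the arm comparison will be biased. The documents support neither as fact. The understatement is zero if no patient with recall is blank, or if the AE form catches all who are, and nothing shows that non-response will differ by arm. Nor do they single recall out as a key outcome: it is item 11 of 12 secondary outcomes. The primary outcome is unaffected.

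**What to change.** Revise the paralysis-recall entry in SAP Appendix A3:

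1. Define when a Brice form is open, and say whether a form created but not completed qualifies.
2. Code NO only for an answered No or a valid skip. Leave other blanks missing.
3. Base the main rate and Fisher's exact test on patients with a determinable Brice answer.
4. Report recall known only from the AE form (no determinable Brice answer) separately by arm, without adding those patients to the main denominator.
5. Show the number not assessable by arm.
6. Keep missing-as-NO, with AE-reported cases counted, as a sensitivity analysis, and add a best-case/worst-case bound. The bound informs only if blanks are few. With 1000 forms, p = 2% and no AE reports, it runs from 19/1000 = 1.9% to 69/1000 = 6.9% at 5% blank, and from 14/1000 = 1.4% to 314/1000 = 31.4% at 30% blank.

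The cost is SAP wording, a slightly smaller denominator and an extra table row, with no new data collection and no change to patient care.

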### Long Term Outcomes

#### Disability: using Katz Activities of Daily Living (ADL)/Lawton Instrumental Activities of Daily Living Scale (IADL) plus two additional Nagi items

ADL/IADL assessments are administered at baseline, months 3, 6 and 12. 2 additional NAGI items were collected at months 3, 6, and 12. The total score is a summation of the all the times. Possible 8 maximum points at baseline and 10 maximum points at follow up. Any missing items are allotted 0 points.

#### Health-Related Quality of Life (including utilities): EuroQol (EQ-5D-5L)

EQ-5D-5L assessment is given to either the subject or the proxy at baseline, month 3, month 6 and month 12. Scores are calculated by mapping the 5-digit code generated from the answers to the U.S. EQ-5D-5L lookup table. Any missing items will result in a missing score.

#### Self-rated health: 1 standard item

Assessed at months 3, 6, and 12 and only if the patient is available.

#### Pain-interference: 1 standard item

Assessed at months 3, 6, and 12 and only if the patient is available.

#### Post-traumatic Stress-like Symptoms: Post-Traumatic Stress Symptoms (PTSS-14)

Assessed at months 3, 6, and 12 by the subject or the proxy. Part A score was calculated as a sum of all the questions answered as "Yes". The part B score was a sum of all the answers (rated from 1 to 7) with a maximum score ranging from 14 to 98.

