## 6.4 ASSESSMENTS AFTER HOSPITALIZATION

These domains and instruments to assess after hospitalization status were selected by the PETAL Neuromuscular Blockade Protocol Committee in conjunction with the PETAL Long-Term Outcomes Committee.

We will assess seven measures after hospitalization:

1. Disability: using Katz Activities of Daily Living (ADL)/Lawton Instrumental Activities of Daily Living Scale (IADL) plus two additional Nagi items
2. Health-Related Quality of Life (including utilities): EuroQol (EQ-5D-5L)
3. Self-rated health: 1 standard item
4. Pain-interference: 1 standard item
5. Post-traumatic Stress-like Symptoms: Post-Traumatic Stress Symptoms (PTSS-14)
6. Cognitive function: Montreal Cognitive Assessment (MoCA-Blind) or, via proxy, the Alzheimer's Disease 8 (AD8)
7. Subsequent return to work, hospital and ED use, and location of residence

These measures will be collected through telephone interviews with patients or their LARs (Appendix G). Informed consent process will include text to facilitate future ancillary long term follow up studies and data collection. All will be obtained at 3, 6, and 12 months except for post-traumatic stress-like symptoms, which will only be obtained at 6 and 12 months. All will be obtained in English or Spanish, from the patient wherever possible. Most will be obtained from proxies when necessary, except as noted for self-rated health, pain interference and post-traumatic stress-like symptoms.

The assessments after follow-up will provide information about post-discharge deaths faster than is available from other sources, although the National Death Index will be used to verify date of death whenever possible (see below).

The Katz ADL is associated with multiple health outcomes among community-dwelling elders[36], and valid among nursing home residents[37]. The Lawton IADL is probably the most widely used self-report or informant-report IADL instrument. These assess a range of common functional activities, from walking and toileting to managing money and cooking meals. We will use the precise wordings from the NIA-funded Health and Retirement Study for which US (and international) norms are available. These scales have been specifically shown to perform well when assessed by proxies for ICU survivors. [40] We will remove the 3 ADL/IADL items that are duplicative of the EQ-5D questions (using the EQ-5D instead), and will add two items from the Nagi scale [41]as implemented in the HRS.

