The EQ-5D[44] has US utilities[45] and is recommended for measurement of health-related quality of life among critical illness survivors.[46] It is quick and feasible in individuals with inattention and fatigue[47]. We will use the EQ-5D-5L version currently used by both the ANZIC RC in Australia and New Zealand and ICNARC in the United Kingdom. We will not use the Visual Analog Scale as these follow-ups will be phone administered and the VAS is not necessary for health economic analysis.

Self-rated health and pain-interference are two common single-item scales that are widely used. We will use the wordings from the SF-12. Because of the highly subjective nature of these domains, these will only be assessed by self-respondents.

The Montreal Cognitive Assessment (MoCA) appears superior to the mini mental status examination and its derivatives for neurocognition assessment in critical illness survivors [48-51], and allows rapid, reliable determination of cognitive impairment [52] in various clinical syndromes.[51, 53-55] The MOCA-Blind version is developed for phone administration. Among community-dwelling older individuals, MoCA scores were lower (more impairment) among patients with elevated levels of inflammatory cytokines. When patients are not able to respond themselves, the validated AD-8 [56]will be used to assess cognitive function by proxy.

We will capture return to work status using the Improving Care of ALI Patients (ICAP) study questionnaire.[59] The Improving Care of Acute Lung Injury Patients employment instrument (ICAP-12) was designed to determine pre- and post-morbid employment status in a multi-center observational study of ARDS survivors[59, 60] and used externally in the NHLBI ARDS Network's ARDS Long-term Outcomes Study (ALTOS) cohorts[61, 62]. We will also ask about recent hospital and Emergency Department use, and whether the patient is residing in a nursing home, at home, or elsewhere.

We will also verify duration of survival for patients lost to follow-up or noted to have died using the Centers for Disease Control and Prevention's National Death Index (NDI) and other federal databases. We will use each patient's social security number (SSN) for an exact NDI match.

We will also collect the patient's Medicare identification number for patients in Medicare to allow assessment of post-discharge health care utilization without any respondent burden back on the

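### The SAP's definition of PTSS-14 adds a month-3 assessment and proxy respondents that protocol section 6.4 rules out; the two need to be reconciled before the analysis set is fixed

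*SAP*

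**What the plan says.** Protocol section 6.4 gives a common schedule of 3, 6 and 12 months for the post-hospital measures, "except for post-traumatic stress-like symptoms, which will only be obtained at 6 and 12 months". On who may answer, it says: "Most will be obtained from proxies when necessary, except as noted for self-rated health, pain interference and post-traumatic stress-like symptoms".

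SAP Appendix A3 defines the same scale differently on both counts: "Assessed at months 3, 6, and 12 by the subject or the proxy". It then describes a Part A count of positive answers and a Part B sum of ratings from 1 to 7, with a range of 14 to 98.

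In SAP Appendix A1 the analysis row for PTSS-14 is binary (Part B score of 45 or more) with a chi-square test. It gives no visit and no respondent restriction.

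For self-rated health and pain interference, the other two measures in the protocol's proxy exception, Appendix A3 limits assessment to occasions when the patient is available.

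**The concern.** The SAP decides which records feed each endpoint. Here its definition is wider than the protocol's data collection in two ways: an additional visit, and an additional class of respondent. The PTSS-14 concerns the respondent's own experience, and a proxy's rating of it can place a patient on the other side of the cut-off from where the patient's own answers would.

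The outcome also has a particular role in this trial. Protocol section 3.6, item 6, counts the absence of data on post-traumatic stress symptoms among the shortcomings of the earlier trial that motivated this one. An ambiguous rule for the scale meant to fill that gap leaves the analyst a choice that should be settled in advance. A month-3 comparison would also be a further test, at the 0.05 level and with no multiplicity correction (SAP section 2.3), at a time when the protocol does not collect the scale.

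**Working it through.** No sample size, power or error-rate figure is involved, so the check is a comparison of texts.

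| Item | Protocol 6.4 | SAP Appendix A3 | Difference |
|---|---|---|---|
| PTSS-14 visits | months 6, 12 | months 3, 6, 12 | month 3 extra in SAP |
| PTSS-14 respondent | excepted from proxy collection | subject or proxy | proxy extra in SAP |
| Self-rated health, respondent | excepted from proxy collection | patient only | none |
| Pain interference, respondent | excepted from proxy collection | patient only | none |

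1. Visits. {3, 6, 12} less {6, 12} leaves {3}, so 1 of the SAP's 3 PTSS-14 visits has no counterpart in the protocol.

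2. Respondents. The protocol names three measures in its exception. The SAP carries the restriction over for 2 of the 3 and drops it for PTSS-14, where it writes "by the subject or the proxy". That pattern suggests a drafting slip, but the SAP neither mentions nor explains a change.

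3. General against specific. Section 6.4 also says of all seven measures: "These measures will be collected through telephone interviews with patients or their LARs". Read alone, this would allow a representative to answer the PTSS-14. The later sentence in the same section deals with proxies measure by measure and takes this scale out, so the specific exception governs.

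4. Route to the analysis. Part B runs from 14 × 1 = 14 to 14 × 7 = 98 and is cut at 45. Because Appendix A1 does not restrict visit or respondent, any month-3 or proxy score in the database qualifies for the chi-square comparison under the Appendix A3 definition.

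5. Size. With s subject-reported and p proxy-reported scores at a visit, the share contrary to the protocol is p / (s + p). Neither document gives s, p or a proxy-interview rate, so the share cannot be computed. If sites kept to section 6.4, p = 0 and there are no month-3 scores.

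**The case against.** The strongest reply is that a sentence in a SAP does not collect data. If sites followed the protocol, no month-3 or proxy scores exist and the inconsistency changes no result. That is correct, and it is why no effect on a result is claimed. The rule still has to be settled, because it says which records count if such scores are present.

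A second reply is that the SAP may be right about the data: Appendix A3 describes the scoring in the past tense and may record what was actually done. The documents do not settle this. It bears on the fix, which has to allow for month-3 or proxy scores already collected.

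Third, the no-proxy rule for PTSS-14 rests on one clause. The protocol's fuller explanation, "Because of the highly subjective nature of these domains, these will only be assessed by self-respondents", follows the description of self-rated health and pain interference and does not extend to PTSS-14. A reader might take it as a rule for every subjective domain; the text does not support that. The clause quoted above names PTSS-14 and is sufficient without it.

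A reader might also infer that proxies stand in for the sickest survivors, so that error would differ between arms. The documents say only that proxies are used when needed, when patients cannot respond themselves, or (for the AD8) when the subject cannot be contacted. None of these is a measure of severity. The trial is unblinded, so unequal error cannot be excluded, but nothing shows that it would occur or in which direction.

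Finally, it would be too strong to say that the SAP specifies a month-3 test of PTSS-14. Appendix A3 defines the variable; the Appendix A1 analysis row names no visit.

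**Conclusion.** The point holds as a direct, unexplained contradiction between SAP Appendix A3 and protocol section 6.4 on both visit and respondent. As the SAP stands, month-3 or proxy PTSS-14 scores, if collected, would count towards the Part B endpoint contrary to the protocol.

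The reach is limited. It touches one of seven long-term measures, within one of twelve secondary outcomes; the primary outcome, sample size, overall error rate and stopping boundaries are unaffected. The number of scores involved is unknown and may be zero. The conclusion rests on reading the protocol's specific exception as overriding its general statement about patients or representatives. It should be corrected, because the outcome addresses a harm the protocol says was left unmeasured and the correction is small.

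**What to change.** Amend the PTSS-14 entry in SAP Appendix A3 so that the analysis uses subject-reported scores at months 6 and 12 only. Repeat the visits and the respondent restriction in the Appendix A1 row. Treat an interview completed only by a proxy as missing for PTSS-14, and cover it with the sensitivity analysis of the missing-at-random assumption in SAP section 2.8. That section triggers the analysis only when the missing proportion is high and sets no threshold, so the entry should say that it will be run for this scale.

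If month-3 or proxy scores were in fact collected, say so, state that this departs from protocol section 6.4, and report those scores separately from the subject-reported 6- and 12-month comparison.

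The drafting cost is a few lines. The statistical cost is fewer analysed scores, and missingness that may be related to health status if patients who cannot answer for themselves differ from those who can. That is why the sensitivity analysis belongs with the change.
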